## 8.2 Pregnancy

Pregnancy and pregnancy outcome will be recorded on the eCRFs. For co-infected participants, pregnancies that occur on study should be reported prospectively to The Antiretroviral Pregnancy Registry. More information is available at [www.apregistry.com](http://www.apregistry.com). [contact]; [contact]. (For studies conducted at sites outside the United States, report to The Antiretroviral Pregnancy Registry—[contact]; [contact] or [contact].)

### Pregnancy Outcomes and Reporting

If a woman has completed the study or chooses to discontinue from the study before the end of the pregnancy, then site staff should request permission to contact her regarding pregnancy outcomes at the end of pregnancy. If the information is obtained, pregnancy outcomes will be submitted on an eCRF at the end of the pregnancy.

Pregnancy will result in immediate discontinuation of the study drugs and initiation of counseling regarding the lack of information of safety in pregnancy with G/P and for those in Step 2 receiving RBV, regarding the teratogenicity of RBV. Participants who become pregnant while on study will be followed on study/off treatment until study completion. A visit 6 months following the end of pregnancy will be conducted for evidence of AEs in the participant and infant, and an outcome eCRF will be completed.

In Step 2, male participants taking RBV whose partners become pregnant will undergo treatment discontinuation and remain on study for continued follow-up until the end of the study. They will receive counseling on RBV teratogenicity and the same follow-up visit at 6 months after their partners' delivery as outlined for pregnant women. This same risk of teratogenicity is not seen with G/P, thus pregnancy of female partner in Step 1 is not an indication for treatment discontinuation.

All participants including female partners of male participants who become pregnant while taking the study treatment will have their pregnancy reported to AbbVie via the sponsor.

If a female participant or male participant with a pregnant female partner has completed the study or chooses to discontinue from the study before the end of the pregnancy, site staff should request permission to contact the female participant or male participant with a pregnant female partner regarding pregnancy outcomes at the end of pregnancy. If the information is obtained, pregnancy outcomes will be submitted on an eCRF at the end of the pregnancy.

## 9.0 CRITERIA FOR DISCONTINUATION

### 9.1 Premature Treatment Discontinuation

- Drug-related toxicity (see [section 8.1](#)).
- Pregnancy in a female participant.
- Participant request to discontinue for any reason.
- Requirement for prohibited concomitant medications (see [section 5.4](#)).
- Breastfeeding.
- Clinical reasons believed life threatening by the physician, even if not addressed in the toxicity section of the protocol.
- For Step 2 only: Pregnancy in female partner of a male participant taking RBV.
- HCV virologic failure during Step 2 (see [section 6.2.6](#)).

NOTE: It is important to determine whether the treatment discontinuation is primarily due to an AE, lack of efficacy, or other reason.

## 9.2 Premature Study Discontinuation

- Request by the participant to withdraw.
- At the discretion of the ACTG, IRB/EC, FDA, NIAID, Office for Human Research Protections (OHRP), any other government agency as part of their duties, investigator, or industry supporter.
- The Study Monitoring Committee (SMC) recommends that the study be stopped early.

## 10.0 STATISTICAL CONSIDERATIONS

### 10.1 General Design Issues

A5380 is a prospective, phase II, single-arm study in treatment of acute HCV infection in participants with and without HIV-1 coinfection. The study will enroll participants at US and non-US sites. The key study objective is to evaluate the efficacy of a 4-week treatment of a FDC of glecaprevir/pibrentasvir (G/P), using SVR12 as the primary outcome measure. SVR12 is defined as unquantifiable HCV RNA at 12 weeks after treatment discontinuation (week 16 visit).

The study is designed to conclude with reasonable evidence that the true SVR12 proportion is greater than 80% in the study population. This will be assessed by examining if a two-sided 90% confidence interval (CI) for the sample proportion is entirely above 80%. This is equivalent to showing that the SVR12 proportion is higher than 80% in a one-sided test with a type I error of 5%, where the aim is to rule out SVR12 proportions below or equal to 80%. The threshold of 80% was chosen based on past studies (see [section 2.2](#)).

The sample size of 44 participants for the evaluation was chosen to provide good power (90%) to show that the SVR12 proportion is not worse than or equal to 80%, assuming that the underlying SVR12 proportion is 95% with the 4-week treatment. The team considers SVR12 proportion of 95% to be plausible based on the results of studies in chronically HCV infected persons using 8 weeks of treatment and considering higher success with acute HCV infection (see [section 2.2](#)). This sample size is deemed to provide reasonable precision around the estimated SVR12 proportion to provide useful information in the treatment of acute HCV.

The primary analysis on SVR12 will include all participants who initiate the treatment. As such, participants who discontinue the treatment early for whatever reason will be included in the primary analysis. Similar to the recently completed acute HCV study conducted in the ACTG (A5327), not achieving unquantifiable HCV RNA at the study visit corresponding to the SVR12 evaluation will be considered failure for SVR12 determination in the primary analysis, regardless of the reason. By this definition, early discontinuation of the study prior to the SVR12 visit will be considered a failure

regardless of the reason, and re-infection prior to the SVR12 visit will also be considered a failure. Understanding reasons for SVR failure is important, and reasons for SVR failure will be described for the anticipated small number of non-SVRs. In addition, an important secondary analysis will be an SVR12 analysis that excludes participants who discontinue the study prior to the SVR12 evaluation for reasons clearly not related to study treatment and participants who become re-infected prior to when SVR12 can be assessed. Reasons for discontinuation unrelated to study treatment may include: participant moved away, participant cannot get to the clinic, participant cannot be located. To ensure that the study is well-powered for this important secondary analysis, additional participants may be enrolled if the study is still enrolling participants when the team becomes aware of such early study discontinuations. The maximum replacement number will be 6 for the study, so that study enrollment will not be greater than 50.

The primary outcome at 12 weeks after treatment discontinuation (week 16) may be evaluated for each participant prior to the completion of study. The primary analysis timeline will be driven by the last participant's completion of the primary outcome visit, rather than the study completion date. Results from the primary analysis on SVR12 may be presented publicly, for example at a conference, when the data related to such analysis are complete, prior to study database finalization.

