### 10.4 Sample Size and Accrual

The sample size was determined to provide good power to show that SVR12 proportion is greater than 80%. The true SVR12 proportion is assumed to be 95% when treated with 4 weeks of the G/P regimen. With 44 participants, there is at least 90% power to show that proportion achieving SVR12 is greater than 80% in a one-sided exact binomial test with a targeted significance level of 5%. [Table 10.4-1](#) below shows the study power for a range of values for the underlying SVR12 proportion.

Table 10.4-1: Study Power for the Underlying SVR12 Proportion

True SVR12 Proportion	Power
90%	54%
92%	72%
95%	93%
97%	99%

With a sample size of 44 participants, the Wilson confidence interval for the true SVR12 proportion will be entirely above 80% if 40 or more participants achieve SVR12 out of 44 participants. The table 10.4-2 below shows two-sided 90% CIs for various potential observed SVR12 proportions in a sample of 44 participants. The width of the CI indicates precision around the SVR12 estimate.

Table 10.4-2: CIs for Various Potential Observed SVR12 Proportions

Observed SVR12 Proportion	90% CI for the True SVR12 Proportion
86.4% (38/44)	(75.7%, 92.8%)
88.6% (39/44)	(78.4%, 94.4%)
90.9% (40/44)	(81.2%, 95.9%)
93.2% (41/44)	(84.1%, 97.2%)
95.5% (42/44)	(87.2%, 98.5%)
97.7% (43/44)	(90.4%, 99.5%)

Accrual of about three participants per month is expected, to complete enrollment in 15 months. Should accrual of additional participants be needed for a key secondary analysis on SVR12, which excludes participants who are re-infected with HCV or discontinue early for reasons not related to study treatment (see [section 10.1](#)), the enrollment period may be extended.

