### 10.6 Analyses

The primary efficacy objective will be addressed by estimating the proportion of participants who achieve SVR12 ([section 10.2.1.1](#) describes this primary endpoint). All enrolled participants who receive any study treatment will be included in the primary analysis. A two-sided 90% CI will be calculated around the estimated SVR12 proportion using the Wilson method for binomial data. If this CI is entirely above 80%, then it will be concluded that there is evidence that the underlying SVR12 proportion is greater than 80%.

For the primary safety analysis, the AEs occurring after initiation of study treatment through the study visit occurring 4 weeks after the treatment completion will be summarized. The proportion of study participants with AEs will be estimated with a two-sided 95% CI around the estimate. As a secondary analysis, all reported AEs (which include events that occur after the time frame defined for the primary safety analysis) will be summarized. A two-sided 95% CI will also be provided for the proportion of study participants with AEs. The Wilson method will be used.

As a secondary analysis, SVR12 will be assessed in the analysis set that excludes participants who discontinued the study early for reasons clearly not related to the study

treatment and participants who became re-infected with HCV prior to SVR12 visit. Reasons not related to study treatment include: participant moved away, participant cannot get to the clinic, participant cannot be located. The analysis will use methods similar to the primary analysis. SVR12 results will also be described separately by HIV-1 infection status.

The secondary HCV RNA endpoints (HCV RNA <LLOQ at study visits) will also be assessed with proportion estimates with two-sided 90% CI using the Wilson method, similar to the primary efficacy analysis on SVR12.

Tolerability failures and virologic failures, as defined in [section 10.2.2](#), will be listed and described. A tolerability failure listing will be accompanied by treatment duration and the associated AE(s). Listings on virologic failure will be accompanied by HCV RNA results and any available information on HCV genotype/subtype, RAS and phylogenetic results.

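### Does the Wilson 90% interval rule break the stated 5% type I error once enrolment can exceed 44?

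*Protocol*

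**What the plan says.** Protocol 10.1 sets the decision by "examining if a two-sided 90% confidence interval (CI) for the sample proportion is entirely above 80"%, and describes this as follows: "This is equivalent to showing that the SVR12 proportion is higher than 80% in a one-sided test with a type I error of 5"%. The values it wants to exclude are 80% and anything lower. SAP 2.4 repeats the equivalence.

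The interval method is given in Protocol 10.6: "A two-sided 90% CI will be calculated around the estimated SVR12 proportion using the Wilson method for binomial data". SAP 4.2 also names Wilson, and SAP 5, item 9a, attaches the conclusion to that interval.

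The exact test appears in the sample size text, Protocol 10.4 (and SAP 2.4), which puts power for 44 enrolled at no less than 90%. That power is computed "in a one-sided exact binomial test with a targeted significance level of 5"%. The assumption there is: "The true SVR12 proportion is assumed to be 95% when treated with 4 weeks of the G/P regimen". The same section states the Wilson cut-off for 44 participants, which is 40 successes.

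The Schema and Protocol 10.1 set a minimum of 44 and a maximum of 50. Up to six participants may be added for those lost for reasons unrelated to treatment; Protocol 10.4 also mentions re-infections. Protocol 10.1 counts both groups as failures in the primary analysis. The supplementary analysis leaves them out.

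**The concern.** A Wilson interval inverts an approximate test, whereas the power was computed with an exact one. For a discrete outcome the two need not give the same cut-off, and the actual error of the Wilson rule moves above and below 5% as N changes. N may end anywhere from 44 to 50, and the supplementary set may be smaller than 44, yet the plan gives a cut-off for 44 only.

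Taken at fixed N, some results pass the Wilson rule and fail the exact test: 43/48, 44/49, 38/42 and 39/43. The trial has no control arm and its efficacy conclusion is one yes-or-no statement. If the plan really contained two success rules that disagreed at borderline counts, the choice between them could be made after seeing the data, and the 5% claim would not describe the rule in use.

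**Working it through.** **Inputs.** Null 0.80, alternative 0.95, planned N = 44, cut-off 40 (Protocol 10.1 and 10.4); Wilson 90% interval, z = 1.645 (Protocol 10.6); maximum N = 50 (Schema, Protocol 10.1).

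**1. The plan's own figures.** The Wilson lower limit is

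L = [p̂ + z²/(2n) − z√(p̂(1−p̂)/n + z²/(4n²))] / (1 + z²/n).

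For 40/44: (0.9091 + 0.0308 − 1.645 × 0.0472) / 1.0615 = 0.812. For 39/44, L = 0.784. Both match Table 10.4-2, and the cut-off of 40 is right.

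Power is P(X ≥ 40 | 44, p): 54.7%, 72.6%, 93.3% and 99.0% at p = 0.90, 0.92, 0.95 and 0.97. The plan states 54%, 72%, 93% and 99%. The exact error is P(X ≥ 40 | 44, 0.80) = 4.40%; with 39 it would be 10.2%, so the exact test also needs 40.

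**2. Is the equivalence true?** L > 0.80 holds exactly when (p̂ − 0.80)/√(0.80 × 0.20/n) > 1.645. That is the one-sided 5% score test. For 40/44 the statistic is 0.1091/0.0603 = 1.81 (pass); for 39/44 it is 1.43 (fail). The sentence in Protocol 10.1 says a one-sided test, not an exact one, and is correct at the nominal level.

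**3. Fixed N.** Cut-offs, with exact error P(X ≥ cut-off | N, 0.80):

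| N | Wilson cut-off | Error | Exact cut-off | Error |
|---|---|---|---|---|
| 42 | 38 | 5.80% | 39 | 2.08% |
| 43 | 39 | 5.06% | 40 | 1.78% |
| 44 | 40 | 4.40% | 40 | 4.40% |
| 45 | 41 | 3.82% | 41 | 3.82% |
| 46 | 42 | 3.32% | 42 | 3.32% |
| 47 | 43 | 2.87% | 43 | 2.87% |
| 48 | 43 | 6.21% | 44 | 2.48% |
| 49 | 44 | 5.47% | 45 | 2.14% |
| 50 | 45 | 4.80% | 45 | 4.80% |

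**4. The route the plan describes.** The 6.21% assumes that 48 was fixed in advance and that each of the 48 could succeed. Under the plan, N = 48 arises because four participants were lost and replaced, and those four are failures. Passing with 43/48 then needs at least 43 successes among the other 44. That probability is 0.07% if their true rate is 0.80, and 1.9% if it is 38.4/44 = 0.873, which makes the overall expected rate 80%. For 44/49 (44 of 44) the figures are 0.005% and 0.6%.

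These condition on the number lost, so the fair measure is the error over all final N. Let d be the chance that a participant is lost and replaced. The plan gives no d, so I assume 0% to 10%. Enrol until 44 are evaluable or 50 are enrolled, with q = 0.80/(1−d) among the evaluable, so that the overall rate is exactly 80%. With c(N) the Wilson cut-off,

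error = Σ(k=0..6) C(43+k, k) dᵏ(1−d)⁴⁴ P(Bin(44, q) ≥ c(44+k)) + Σ(m<44) C(50, m)(1−d)ᵐ d⁵⁰⁻ᵐ P(Bin(m, q) ≥ 45).

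This gives 4.4% at d = 0, 4.2% at 2%, 3.9% at 5%, 3.8% at 8% and 4.0% at 10%.

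**5. Supplementary set.** Use q = 0.80 and the Wilson cut-off for the number evaluable. With replacement as above, the error is 4.4% to 4.5% for d = 2% to 10%. If nobody is replaced (44 enrolled, losses excluded), it is 4.8% at d = 2%, 4.3% at 5% and 3.7% at 10%. N = 42 and 43 do occur, but so do smaller N with errors well below 5%.

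**The case for a change.** The strongest case is that SAP 2.4 puts the equivalence claim, the exact test and the Wilson cut-off in one paragraph, as if they were one rule, and that no cut-off is given for other N. If the final N were 48 or 49 for some reason other than replacement, or if only 42 or 43 of those enrolled started treatment, the fixed-N errors in the table would apply. One named method for both power and decision would be tidier.

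The arithmetic in that case stands. Two things limit it. The plan describes no route to 48 or 49 other than replacement, and Protocol 6.2.2 has treatment start within 24 hours of registration with the first dose observed, so few untreated enrolees are to be expected. Even then the excess is at most 1.2 points. There is also no open choice of rule: every decision statement uses the Wilson interval, and the exact test is tied to the power at 44. For the supplementary set, Protocol 10.6 asks for methods similar to the primary, but the explicit conclusion about 80% is attached to the primary analysis and no 5% claim is made for the other.

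Nor is the exact method a free improvement. At a true rate of 95%, its power in the supplementary set is 84.3% at N = 42 and 83.3% at N = 43, against 94.3% and 93.8% with Wilson. Protocol 10.1 wants that analysis to be well powered.

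**Conclusion.** The concern does not hold. The plan has one success rule, the Wilson interval, and its stated equivalence to a one-sided 5% test is correct at the nominal level. At the planned 44 the Wilson and exact methods coincide (40 successes, actual error 4.4%, power 93%), and the plan's cut-off, power table and interval table all reproduce. Along the enrolment route the plan describes, the primary error is 3.8% to 4.4% and the supplementary error at most 4.8%. The 6.2% figure requires N = 48 to be fixed in advance with no built-in failures, for which the plan has no mechanism.

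This rests on three assumptions: enrolment passes 44 only to make up for participants who count as primary failures; the share lost is 0% to 10% for the primary figure and 2% to 10% for the supplementary one; and outcomes are independent between participants. What remains is the ordinary movement of a Wilson rule's actual error around its nominal level. Preferring an exact rule is a choice of method and corrects no error.

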## 10.2 Outcome Measures

Primary and secondary outcome measures listed below will be addressed in the study's primary Statistical Analysis Plan, which will define the content of the Primary Analysis Report. This report will form the basis for the primary study manuscript and results reporting to [ClinicalTrials.gov](#). Outcomes of interest for secondary and exploratory objectives intended for subsequent publications are to be listed under "Other Outcome Measures".

### 10.2.1 Primary Outcome Measures

- 10.2.1.1 SVR12 defined as achieving unquantifiable HCV RNA (<LLOQ TD or TND) at the study visit occurring at 12 weeks after treatment discontinuation (week 16). The sample within the visit window for week 12, as defined in [section 6.0](#), will be used. If a participant does not have any HCV RNA measurements in this time period then the participant will be considered as SVR12 failure, unless there are preceding and subsequent HCV RNA measurements that are both LLOQ (either TD or TND).
- 10.2.1.2 Any reported AE occurring after initiation of study treatment through the study visit occurring 4 weeks after the treatment completion.
- 10.2.1.3 Tolerability, defined as completion of 4 weeks of treatment without discontinuation due to AEs.

### 10.2.2 Secondary Outcome Measures

- 10.2.2.1 HCV RNA <LLOQ (TD or TND) at study visits, using the visit windows as defined in [section 6.0](#).
- 10.2.2.2 Virologic failure, defined as failure to achieve unquantifiable HCV RNA and confirmed increase in HCV RNA  $>1 \log_{10}$  from on-treatment nadir.

### 10.2.3 Other Outcome Measures

- 10.2.3.1 Re-infection, defined as confirmed quantifiable HCV RNA during follow-up after achieving unquantifiable HCV RNA at the end of treatment or during follow-up, with phylogenetic results supporting new infection.
- 10.2.3.2 Relapse, defined as confirmed quantifiable HCV RNA during follow-up after achieving unquantifiable HCV RNA at the end of treatment or during follow-up, with phylogenetic results excluding new infection.
- 10.2.3.3 HCV resistance profile at study entry. The set of mutations to be considered will be defined prior to analysis based on the latest information.
- 10.2.3.4 Development of HCV resistance mutation(s) in SVR12 failures.
- 10.2.3.5 SVR12 for re-treatment, defined as achieving unquantifiable HCV RNA (<LLOQ TD or TND) at the study visit occurring at 12 weeks after treatment discontinuation For the participants receiving 8 weeks of re-treatment, study visit at Step 2 week R+20 will be used for SVR12 evaluation. For the participants receiving 12 weeks of re-treatment, study visit at Step 2 week R+24 will be used for SVR12 evaluation. For the participants receiving 16 weeks of re-treatment, Step 2 week R+28 will be used for the SVR12 evaluation.
- 10.2.2.6 Substance use.
- 10.2.2.7 Self-reported adherence measured by the number of missed doses.
- 10.2.2.8 Adherence measured by the pill count.
- 10.2.3.9 Serologic and virologic markers of acute immunologic host response (to be defined at the time of assay determination).
- 10.2.3.10 CD4+ T-cell recovery (to be defined at the time of assay determination).

10.2.3.11 Type I IFN-induced immune dysfunction (to be defined at the time of assay determination).

10.2.3.12 Cost-effectiveness measure (to be determined by assessing the resource use and cost of care).

### 10.3 Randomization

There is no randomization in this study. All enrolled participants will receive the study treatment. The minimum number of HIV-1-infected participants is 10, and there is no maximum.

### 10.4 Sample Size and Accrual

The sample size was determined to provide good power to show that SVR12 proportion is greater than 80%. The true SVR12 proportion is assumed to be 95% when treated with 4 weeks of the G/P regimen. With 44 participants, there is at least 90% power to show that proportion achieving SVR12 is greater than 80% in a one-sided exact binomial test with a targeted significance level of 5%. [Table 10.4-1](#) below shows the study power for a range of values for the underlying SVR12 proportion.

Table 10.4-1: Study Power for the Underlying SVR12 Proportion

True SVR12 Proportion	Power
90%	54%
92%	72%
95%	93%
97%	99%

With a sample size of 44 participants, the Wilson confidence interval for the true SVR12 proportion will be entirely above 80% if 40 or more participants achieve SVR12 out of 44 participants. The table 10.4-2 below shows two-sided 90% CIs for various potential observed SVR12 proportions in a sample of 44 participants. The width of the CI indicates precision around the SVR12 estimate.

Table 10.4-2: CIs for Various Potential Observed SVR12 Proportions

Observed SVR12 Proportion	90% CI for the True SVR12 Proportion
86.4% (38/44)	(75.7%, 92.8%)
88.6% (39/44)	(78.4%, 94.4%)
90.9% (40/44)	(81.2%, 95.9%)
93.2% (41/44)	(84.1%, 97.2%)
95.5% (42/44)	(87.2%, 98.5%)
97.7% (43/44)	(90.4%, 99.5%)

Accrual of about three participants per month is expected, to complete enrollment in 15 months. Should accrual of additional participants be needed for a key secondary analysis on SVR12, which excludes participants who are re-infected with HCV or discontinue early for reasons not related to study treatment (see [section 10.1](#)), the enrollment period may be extended.

